8.2.2. During the treatment period

S64315 LID period

- Clinical examination:
 - Vital signs (temperature, HR, BP): LID1 and LID2 predose*, LID1 and LID2 End of Infusion (EoI), 2h and 24h after LID1 and LID2 EoI
 - ECOG PS at LID1 predose*

- Laboratory tests:
 - Blood haematology with differential and blood biochemistry (fasted): LID1 and LID2 predose*, 24h and 48h after LID1 and LID2 EoI. A blood haematology sample should be obtained between LID1 and LID2 and between LID2 and C1D1 to ensure WBC are < 10 G/L during the LID period
 - Blood biochemistry limited to AST, ALT and total bilirubin: 8h after LID1 and LID2 EoI
 - Cardiac markers (including troponin, CPK-MB and BNP): LID1 and LID2 predose*, 6h, 24h, 48h and 72h after LID1 and LID2 EoI
 - TLS laboratory parameters monitoring (WBC, creatinine, phosphorus, calcium, potassium, uric acid, LDH): LID1 and LID2 predose*; 2h, 4h, 8h and 24h± 2h after LID1 and LID2 EoI
 - Blood coagulation, thyroid function and urinary analysis at LID1 predose*
- *Predose exams to be performed within 3 days prior to LID1 or LID2
- Triplicate ECGs: see [Table \(8.2\) 2](#)

Cycle 1

- Clinical examination:
 - Vital signs (temperature, HR, BP):
 - D1: azacitidine predose*
 - D2, D9, D16 and D23: S64315 predose*, S64315 EoI and 2h after S64315 EoI
 - ECOG PS on D1 azacitidine predose*
 - Body weight on D1 azacitidine predose*
- Laboratory tests:
 - Blood haematology with differential and blood biochemistry:
 - D1: azacitidine predose*
 - D2: S64315 predose* and EoI
 - D9, D16 and D23: S64315 predose*
 - Blood biochemistry limited to AST, ALT and total bilirubin: 8h, 24h and 72h after S64315 C1D2 EoI and 24h after C1D9 EoI
 - Blood coagulation, thyroid function and urinary analysis on D1 predose*
 - Cardiac markers (including troponin, CPK-MB and BNP)[#]: D1: azacitidine predose*, D2 and D9: S64315 predose*, 6h, 24h, 48h and 72h after EoI, D16 and D23: S64315 predose*

[#]In case of any troponin increase observed after the two first S64315 infusions of cycle 1, it will be recommended to assess cardiac markers at 48h and 72h after S64315 EoI, and after each subsequent infusion (before discharge and beyond, if needed), on a regular basis according to investigator's judgment.

 - TLS laboratory parameters monitoring (WBC, creatinine, phosphorus, calcium, potassium, uric acid, LDH):
 - D1: predose*, 1h30 and 6h after azacitidine administration
 - D2: predose*, 2h, 4h, 8h, 24h±2h after S64315 EoI

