8.2.9. Tumour Lysis Syndrome management

Tumour Lysis Syndrome (TLS) prophylaxis is required during the administration of S64315 in combination with azacitidine for patients with active disease, in case of intra-patient dose escalation to a new assigned dose(s) and in case of readministration after one or both IMPs interruption \geq 28 days.

Even if only patients with low/intermediate risk of TLS are included, TLS prophylaxis for intermediary risk should be implemented for any patient considering the expected overlapping toxicity of the combination. TLS management will be based on institutional guidelines and published criteria ([Cairo, 2010](#)) and on the recommendations described below.

Hydration

Adequate hydration should be ensured for all patients according to routine clinical practice and international guidelines (Cairo, 2010).

In order to prevent the risk of TLS, hydration will be made mandatory during the LID period and during the two first infusions of S64315 at the full tested dose (LID1, LID2, C1D2 and C1D9). Patients should be encouraged to drink up to 1.5 to 2.0 L of water daily starting the day before the S64315 infusion, and 24 hours after. Intravenous fluids at 50cc/hour or higher are recommended to be administered for at least 12 hours prior to the S64315 infusion, then IV fluid should be continued according to the investigator's judgement. The rate of IV fluids should be adjusted per clinical judgment.

Anti-hyperuricaemic agents

Allopurinol is recommended for patients with active disease throughout the study. Patients who develop laboratory TLS should receive rasburicase unless clinically contraindicated (Cairo, 2010).

Laboratory assessments (see section 8.2.2).

Before and following S64315 infusions during the LID period (LID1 on D-13 and LID2 on D-6):

WBC, serum uric acid, serum calcium, serum phosphorus, serum potassium, serum creatinine and LDH must be monitored at the following time points:

- Prior to S64315 administration (LID1 and LID2 predose)
- 2h, 4h and 8h after S64315 EoI (LID1 and LID2)
- 24h (\pm 2h) after S64315 EoI (LID1 and LID2)

Before and following the first azacitidine administration (C1D1) and first S64315 infusion (C1D2) of cycle 1:

WBC, serum uric acid, serum calcium, serum phosphorus, serum potassium, serum creatinine and LDH must be monitored at the following time points:

- Prior to azacitidine first injection (C1D1 predose)
- 1h30 and 6h after azacitidine first injection (C1D1)

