1.2. Study endpoints

The endpoints for the primary objective are:

- The incidence of DLT(s) starting from the lead-in dose (LID) period to the end of each cycle of treatment of S64315 in combination with azacitidine.
- The incidence and severity of adverse events (AEs) and serious adverse events (SAEs) according to the National Cancer Institute Common Terminology Criteria for Adverse Events (NCI-CTCAE) version 5.0.
- The recording of any change or addition of a new concomitant treatment.
- The laboratory tests: haematology with differential, blood biochemistry, thyroid function, blood coagulation, urinary analysis, hepatitis markers, Tumour Lysis Syndrome (TLS) monitoring, cardiac markers follow up.
- The complete physical examination, Eastern Cooperative Oncology Group (ECOG) performance status and vital signs measurements.
- The electrocardiogram (ECG) parameters and cardiac function assessment.
- The left ventricular ejection fraction (LVEF).
- The dose interruptions, reductions and dose intensity.

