3.4.4. Clinical laboratory evaluation

Descriptive statistics on quantitative value and value by grade at baseline and worst grade on treatment according to the grade at baseline will be provided for gradable parameters (see [Table \(3.4.4\) 1](#)).

Table (3.4.4) 1 – Gradable parameters

Parameter		Worst Highest	Worst lowest	Gradable at baseline*
Blood biochemistry	Alanine aminotransferase (ALT)	High ALT	NA	No
	Albumin	NA	Low albumin	Yes
	Alkaline phosphatase (ALP)	High ALP	NA	No
	Amylase	High amylase	NA	Yes
	Aspartate aminotransferase (AST)	High AST	NA	No
	Bilirubin (total)	High total bilirubin	NA	No
	Cholesterol (total)	High cholesterol	NA	Yes
	Creatine phosphokinase (CPK)	High CPK	NA	Yes
	Gamma-glutamyl transferase (gamma-glutamyl transpeptidase) (GGT)	High GGT	NA	No
	Creatinine (serum)	High serum creatinine	NA	Yes
	Glucose	NA	Hypoglycemia	Yes
	Lypase	High lipase	NA	Yes
	Magnesium	Hypermagnesemia	Hypomagnesemia	Yes
	Potassium	Hyperkalemia	Hypokalemia	Yes
	Sodium	Hypernatremia	Hyponatremia	Yes
	Triglycerides	High triglycerides	NA	Yes
	Ionized calcium	High ionized calcium	Low ionized calcium	Yes
Blood haematology	Haemoglobin	High haemoglobin	Anemia	Yes for Low / No for High
	Lymphocytes	NA	Low lymphocytes	Yes
	Neutrophils	NA	Low neutrophils	Yes
	White blood cells (WBC)	NA	Low WBC	Yes

	Platelets	NA	Low platelets	Yes
Blood coagulation	Activated partial thromboplastin time (aPTT)	High aPTT	NA	Yes

Descriptive statistics on quantitative value and value by reference ranges at baseline and worst value on treatment according to baseline, with respect to the lower-limit normal (LLN) and the upper-limit normal (ULN) or by classes (<LLN / [LLN-ULN] / >ULN or normal / mild / moderate / severe for creatinine clearance) will be provided for non-gradable parameters (see [Table \(3.4.4\) 2](#)) and for parameters gradable post-baseline but non-gradable at baseline, in which case only baseline values will be presented.

Table (3.4.4) 2 – Non Gradable parameters

Parameter		Worst Highest	Worst lowest
Blood biochemistry	Bicarbonates	NA	Low bicarbonates
	Uric acid	High uric acid	NA
	Calcium (total)	Hypercalcemia	Hypocalcemia
	Creatinine clearance (approximated by the Modification of Diet in Renal Disease Glomerular Filtration Rate (MDRD GFR))	NA	Low creatinine clearance (Normal/mild/moderate/severe)
	Direct bilirubin	High direct bilirubin	NA
	High-density lipoprotein (HDL)	High HDL	NA
	Lactate dehydrogenase (LDH)	High LDH	NA
	Low-density lipoprotein (LDL)	High LDL	NA

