	Phosphorus	NA	Hypophosphatemia
	Troponin I	High troponin I	NA
	Troponin T	High troponin T	NA
	Urea	High urea	NA
	Urea nitrogen (blood) (BUN)	High BUN	NA
Blood haematology	Basophils	NA	Low basophils
	Eosinophils	High eosinophils	NA
	Haematocrit	High haematocrit	Low haematocrit
	Monocytes	High monocytes	NA
	Red Blood Cell (RBC) Count	High RBC	Low RBC
	Lymphocytes	High lymphocytes	NA

	White Blood Cell (WBC) Count	High WBC	NA
Thyroid function	T3 free	High T3 free	Low T3 free
	T4 free	High T4 free	Low T4 free
	Thyroid Stimulating Hormone (TSH)	High TSH	Low TSH
Cardiac markers	Creatine PhosphoKinase Myocardial Band (CPK-MB) activity	High CPK-MB activity	NA
	CPK-MB mass	High CPK-MB mass	NA
	Brain Natriuretic Peptide (BNP)	High BNP	NA
Blood coagulation	International normalized ratio (INR)	High INR	NA

For urinalysis parameters haematuria, glycosuria, proteinuria, ketonuria: Descriptive statistics at baseline and worst value on treatment period, by classes (negative, trace, positive).

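### In SAP Table (3.4.4) 2 phosphorus is the only tumour-lysis panel analyte with no worst-high on-treatment summary

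*SAP*

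**What the plan says.** SAP section 1.2 names, among the laboratory tests that serve as endpoints for the primary objective, "urinary analysis, hepatitis markers, Tumour Lysis Syndrome (TLS) monitoring, cardiac markers follow up".

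The protocol fixes the TLS panel in section 8.2.2 and repeats it in section 8.2.9: "WBC, serum uric acid, serum calcium, serum phosphorus, serum potassium, serum creatinine and LDH must be monitored at the following time points". That is seven analytes.

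SAP section 3.4.4 splits laboratory parameters into gradable (Table (3.4.4) 1) and non-gradable (Table (3.4.4) 2), and each table says whether the worst-highest value, the worst-lowest value or both are analysed. For non-gradable parameters the output is "Descriptive statistics on quantitative value and value by reference ranges at baseline and worst value on treatment according to baseline". Phosphorus is in Table (3.4.4) 2, with NA for worst-highest and "Hypophosphatemia" for worst-lowest.

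For tests without CTCAE grades, protocol section 10.4.4.2 plans shift tables from baseline by normal-range class. It does not restrict them to one side of the range.

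**The concern.** Phosphorus is measured repeatedly after the first infusions as part of the TLS panel, yet the SAP asks only for its low side on treatment. Other panel members have a high-side entry, such as "High uric acid" and "Hyperkalemia". The SAP does not explain why phosphorus differs, and the restriction is narrower than what the protocol planned.

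At stake is the completeness of the safety tables. The report is an abbreviated one that drops efficacy and follow-up but keeps the safety profile, so these tables carry much of what will be reported. TLS is listed among the identified risks in protocol Table (8) 1, and reducing that risk is one of the stated aims of the lead-in doses (protocol section 2.3.6).

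**Working it through.** The plan gives no figure to reproduce and no error rate is involved. The check compares the panel with the two SAP tables, then follows a raised value through the SAP rules.

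**Step 1. Direction listed for each panel analyte** (panel from protocol 8.2.2 and 8.2.9; directions from SAP Tables (3.4.4) 1 and 2)

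| Analyte | SAP table | Worst-high listed | Worst-low listed |
|---|---|---|---|
| Potassium | 1 | yes | yes |
| Serum creatinine | 1 | yes | NA |
| Total calcium | 2 | yes | yes |
| Uric acid | 2 | yes | NA |
| LDH | 2 | yes | NA |
| WBC | 2 (high), 1 (low) | yes | yes |
| Phosphorus | 2 | **NA** | yes |

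Worst-high is listed for 6 of 7; phosphorus is the exception. This counts table entries. It is not a count of the direction in which TLS moves each analyte, which the documents do not state.

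**Step 2. What happens to a raised on-treatment value.** Under the worst-value rule in SAP section 4.2.3.4, the low-side variable for a non-gradable parameter takes the result if it is below the lower limit of normal (LLN), and 0 otherwise. Take three patients:

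- always within range: low = 0;
- within range except for one value above ULN after an infusion: low = 0;
- at least one value below LLN: low = the result.

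The first two cannot be told apart. If the lowest value were instead placed in the three reference-range classes of section 3.4.4, a patient would be classed above ULN only when every on-treatment value was above ULN. A transient rise would still be lost.

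**Step 3. Whether another SAP output supplies it.**

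- Baseline phosphorus is shown by class, including above ULN (section 3.4.4), but this is before treatment.
- The TLS section (3.2.4.13) covers preventive treatments, risk category, hydration and anti-hyperuricaemic use. It contains no laboratory results.
- AE tables (3.4.2) include a raised value only if it was reported as an AE. DLT tables (3.4.1) rest on the investigator's report and are not recalculated (4.2.3.1).

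None of these is a systematic on-treatment summary of high phosphorus.

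**Step 4. How many measurements are involved.** Scheduled TLS-panel time points per patient (protocol 8.2.2): predose, 2, 4, 8 and 24 h at LID1, LID2 and C1D2, plus predose, 1 h 30 and 6 h on C1D1. That is 3 × 5 + 3 = 18, before routine biochemistry is counted. If the LID1 predose value serves as baseline, 18 − 1 = 17 are on treatment.

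**The case against.** Several points on the other side are sound.

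- **High values have other routes into the report.** Protocol section 8.2 requires a laboratory abnormality with clinical impact to be reported as an AE, unless it supports a diagnosis already reported as one. The electrolyte DLT criterion names phosphorus without a direction. A reader might infer that high phosphorus is never tabulated anywhere; the documents do not support that. What is missing is the on-treatment laboratory tabulation of high values not reported as an AE or DLT.
- **The cell is not what prevents a laboratory-TLS analysis.** A reader might infer that laboratory TLS could be read from the tables but for this entry. The tables give one worst value per parameter over the treatment period, so they do not show whether several analytes were abnormal in one patient after one infusion. Neither document defines a laboratory-TLS endpoint to derive.
- **The TLS direction for phosphorus is not in the documents.** To say that the table reports the wrong tail would rest on general clinical knowledge. The point does not need it: phosphorus is out of line with the other six analytes and with the protocol's shift tables.
- **The measurements are not wasted.** All on-treatment values enter the worst-low derivation, and the monitoring serves patient care as it happens.
- **The method exists and the shells are unseen.** Section 4.2.3.4 defines the high side as well as the low, and the table shells are in a separate document that may include the output. Table (3.4.4) 2 nevertheless does not ask for it.

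These points limit the reach of the concern. They do not supply the missing summary.

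**Conclusion.** The gap is real and small. One of seven TLS-panel analytes has no worst-high on-treatment summary, and the SAP is narrower here than the protocol without saying why. The consequence is confined to one descriptive table: on-treatment phosphorus above ULN, when not reported as an AE or DLT, merges with normal results. No estimate, DLT count, sample size or dose-escalation rule changes.

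This rests on two assumptions: that the outputs follow Table (3.4.4) 2 as written, and that the separate shells do not add a high-side phosphorus table.

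**What to change.** In SAP Table (3.4.4) 2, replace NA by Hyperphosphatemia under worst-highest for phosphorus, keep the low-side entry, and present both directions as is done for total calcium. Use the high-side derivation already in section 4.2.3.4, and check that the table shells match. With this entry, 7 of 7 panel analytes have a worst-high summary.

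The cost is one table cell and one further output from data already collected: a free improvement. If the sponsor also wants a laboratory-TLS analysis, that is a separate addition needing its own definition; this change does not deliver it.

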3.4.5. Vital signs and clinical examination

Vital signs and clinical examination will be described, in terms of quantitative value and value by classes at baseline, worst (highest and/or lowest) value under treatment, and absolute and change (and relative change for weight as well) from baseline to worst (highest and/or lowest) value under treatment for:

- SBP (<90, [90-140[and ≥ 140 mmHg).
- DBP (<60, [60-90[, ≥ 90 mmHg).
- HR (<60, [60-100[and ≥ 100 bpm).
- ECOG status (0, 1, 2, 3, 4, 5).
- Weight (relative baseline change measured as <-10%, $\geq -10\%$).

3.4.6. Centralised ECG

QT interval (uncorrected and corrected Fridericia) during the treatment period will be described in terms of:

- Maximum absolute prolongation.
- Maximum change from baseline.

Values and changes from baseline of corrected QT interval will be described in classes, considering thresholds defined in ICH E14:

- Values: ≤ 450 , [450-480], [480-500] and > 500 .
- Changes: ≤ 30 , [30-60] and > 60 .

Emergent ECG and emergent clinically significant ECG abnormality during treatment period will be described.

3.4.7. LVEF

LVEF will be described, in terms of quantitative value:

- At baseline.
- Worst (*lowest*) post-baseline value under treatment.
- Change from baseline to worst (lowest) post-baseline value under treatment.

Moreover, values and change from baseline of LVEF will be described in classes:

- Values: <40 / [40-50[/ ≥ 50%.
- Change and relative change: ≤ -10% / > -10%.

The worst (lowest) value under treatment will also be described by grade according to NCI-CTCAE version 5.0 (Grade 0 / Grade 2/ Grade 3 / Grade 4).

3.5. Exploratory analysis

All exploratory biomarker analysis results will be presented in a separate report.

3.6. Interim analysis

N.A.

4. APPENDICES

4.1. General analytic definitions

Definitions below correspond to calculation rules for expressions defined in [Section 3.2](#), [3.3](#), [3.4](#) as well as definition of value prior to treatment / under treatment, analysable value, first and last IMP intake dates and other general definitions.

4.1.1. Expressions

Reliable value

For biological and coagulation samplings:

Identified with flag BIOFG (“Non analysable value”) different from 1 and non-missing result.

For other panels:

Non-missing result.

Value at baseline is defined as the last reliable (i.e. last non-missing) value prior to treatment.

Note: In case of patient included but not treated (i.e. patients with treatment duration equal to 0): value at baseline is defined as the last analysable value prior to the LID (i.e. "Visit<C000").

Baseline value of cycle n is defined as the last reliable (i.e. last non-missing) value prior to first study treatment intake of cycle n.

Value at the Cycle n Day n is defined as the first reliable (i.e. first non-missing) value at the visit.

Post-baseline value is defined as available value after the first IMP intake or, in case of missing first intake, after the date visit superior (>) to last inclusion visit (A000).

End post-baseline value is defined as the last reliable post-baseline value of the criteria of interest during the treatment period.

Worst post-baseline value is defined as the worst reliable post-baseline value of the criteria of interest during the treatment period.

Lowest/highest post-baseline value is defined as the lowest/highest value during the treatment period.

Change from baseline to worst post-baseline value is calculated as:

Worst post-baseline value - Value at baseline.

Change from baseline to lowest/highest post-baseline value is calculated as:

Lowest/highest post-baseline value - Value at baseline.

Relative change from baseline to highest/lowest value (%) is calculated as:

$$\left(\frac{(\text{Highest|Lowest value during the period of interest} - \text{Value at baseline})}{\text{Value at baseline}} \right) * 100.$$

4.1.2. First and last IMP intakes dates

For patients having taken at least one dose of IMP (S64315 or azacitidine), the dates of first and last IMP (S64315 or azacitidine) intake on the analysis period (including LID) will be defined as follows:

- The date of the first IMP intake within the analysis period (including LID).
- The date of the last IMP intake within the analysis period (including LID):
max(last intake date of last cycle of S64315, last intake date of last cycle of azacitidine).

Note: For azacitidine, cycles with both missing first and last IMP intake dates and with administered dose missing or equal to 0 will not be taken into account.

After selection of the dates of first and last IMP intake as defined above, if these dates are missing or incomplete, the following substitution rules will be applied:

Table (4.1.2) 1 - Substitution rules of IMP intake dates

Date to substitute	Substituted date
First IMP (S64315 or azacitidine) intake	
./mmm/yyyy
 
Inclusion date if complete with same month and year Otherwise: 01/mmm/yyyy
 
./.../yyyy
 
Inclusion date if complete with same year Otherwise: 01/JAN/yyyy
 
./.../....
 
Inclusion date if complete

Last IMP (S64315 or azacitidine) intake	
./mmm/yyyy
 
Last available date* if same month and year Otherwise: Last day of the month/mmm/yyyy
 
./.../yyyy
 
Last available date* if same year Otherwise: 31/DEC/yyyy
 
./.../....
 
Last available date* Last available date**

Notes:

- Missing dates will be substituted only for patients having taken at least one dose of study treatment:
./mmm/yyyy = missing day.
./.../yyyy = missing day and month.
./.../.... = totally missing date.
***** Last available date (only for patients included) is defined as date of death if patient died, and as maximum date among completed dates relative to patient's information otherwise.

4.1.3. Value prior to treatment / under treatment

Table (4.1.3) 1 - Time frame

Criteria	Value prior to treatment if measured between (D1=) days before and (D2=) days after the first IMP intake (D1 and D2 included)		Post-baseline value on treatment period if measured between (D1=) days after the first IMP intake and until (D2=) days after the last IMP intake (D1 and D2 included)	
	D1 =	D2 =	D1 =	D2 =
Disease assessment	D1 = 21	D2 = Xsup	D1 = Xinf	D2 = 28
Biochemistry / haematology / thyroid function / coagulation / hepatitis markers	D1 = 21	D2 = Xsup	D1 = Xinf	D2 = 28
Vital signs	D1 = 21	D2 = Xsup	D1 = Xinf	D2 = 28
ECG/LVEF	D1 = 21	D2 = Xsup	D1 = Xinf	D2 = 28
Pregnancy Test	D1 = 21	D2 = Xsup	D1 = Xinf	D2 = 28
All other criteria (death and AE excepted)	D1 = 28	D2 = Xsup	D1 = Xinf	D2 = 28*

Xsup: 0 and "Visit < "***".

Xinf: 0 and "Visit ≥ "***".

(*): 30 days for AE and death analysis.

(**) Visit number depending on the panel

4.1.4. General duration derivation and conversion

In instances where duration or times-to-event are calculated, the convention to be used unless otherwise specified is [later date] – [earlier date] + 1 day.

When converting a number of days to other units, the following conversion factors will be used: 1 year = 365.25 days; 1 month = 30.44 days.

4.1.5. Analysable value

Table (4.1.5) 1 - Definition of analysable value

General definition	
Non missing value	
Specific definitions	
Laboratory parameters	Only reliable values are considered for analyses. Unreliable values are flagged into the database.
ECG parameters	For the analysis of QT criteria per measurement time, only values at each scheduled post-baseline visits will be analysed. All data obtained from triplicate ECGs are taken into account in the analysis. For ECGs, for each measurement time, the mean of available values is calculated and taken into account in the analyses. The measurement times of QT criteria will be those fulfilled in the database and transferred by Banook Group.
PB blasts BM blasts	Having at least 20% blasts in the BM or PB is used for diagnosis of AML. In normal BM the blast count is 5% or less, while PB usually doesn't contain any blasts. PB or BM blast percentages (%) are also monitored for diagnosis, management, and follow up of AML patients. All values [0, 100[are considered for analyses.

